#### **12.4.3 Serum Pharmacodynamic Parameters**

Pharmacodynamic parameters will be computed from the individual raw concentrations of serum calcium (mmol/L) (uncorrected and corrected for serum albumin levels), phosphate (mmol/L), magnesium (mmol/L), 1,25(OH)2D3 (pmol/L) and FGF23 using a non-compartmental approach and actual times. pharmacodynamic parameters will be estimated for both Day -1 and Day 1 in each treatment period. Serum calcium will be corrected for serum albumin levels using the following equation:

Corrected calcium (mmol/L) = serum calcium (mmol/L) + 0.02 (40 - serum albumin (g/L))  
(Parent X1, 2009)

The following parameters will be calculated from the raw serum concentration data using WinNonlin Phoenix version 6.3 or higher (Pharsight Corporation, Mountain View, California, USA):

- AUC0-24h: the area under the concentration versus time curve, from time 0 to 24 hours
- TEmax: time to maximum effect
- Emax: maximum effect
- TEmin: time to minimum effect
- Emin: minimum effect

The same parameters will also be calculated for the calcium-phosphate product.

In addition, serum pharmacodynamic parameters will be estimated based on baseline-adjusted serum concentration of pharmacodynamic markers as follows:

- AUCabove: Area under the concentration-time curve that is above the baseline, from time 0 to 24 hours, as calculated by the linear trapezoidal method
- AUCbelow: Area under the concentration-time curve that is below the baseline, from time 0 to 24 hours, as calculated by the linear trapezoidal method
- AUCnet: AUCabove - AUCbelow
- TEmax: time to maximum effect
- Emax: maximum effect
- TEmin: time to minimum effect
- Emin: minimum effect

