21.	
These changes (item 19 and 20 above) necessitated the reorganization of Table 3 (from the original protocol v 1.0) to be split into 2 separate tables in the amended protocol: Table 3 now summarizes assessments for the QD treatment period, and Table 4 (now added) summarizes assessments for BID treatment period. Subsequent tables in this protocol were renumbered accordingly (ie, Table 4 becomes Table 5, Table 5 becomes Table 6).
 
Reason for change: Clarification to tables.
	Table 3; Table 4 (newly added)

Protocol Amendments		
Summary of Change(s) Since Last Version of Approved Protocol		
Amendment Number	Amendment Date	Global
1	26 Feb 2016	
Item #	Description of Change	Section(s) Affected by Change
22.	
Table 2: Day -1 (Prior to Treatments 1 and 2): Table revised to remove reference relative to BID post evening dose collection time points in the header; streamlined to remove time point/columns where no PD sampling is required.
 
Reason for change: Clarification to table.
	Table 2
23.	
Table 2: Day -1 (Prior to Treatments 1 and 2): PD blood collections were removed at 18, 20, and 22 hours post-dose time points.
 
Reason for change: To correspond to the revised pharmacodynamic sampling time points on Day 1 for QD and BID treatment schedules, and to serve as a baseline (Day -1) comparison for each respective time point on Day 1 of each treatment period. This should enable the assessment and comparisons of the treatment effects on serum calcium and urinary calcium profiles for each of the 6 treatments to their corresponding respective baseline time points.
	Table 2

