**Table 2: Detailed Schedule of Assessments: Day -1 (Prior to Treatment Periods 1 and 2)**

Study Day	-1																		1
Time point (relative to scheduled dosing time on Day 1 [QD, 1st dose BID]) (hour)	Pre-dose	1	1.5	2	3	4	6	8	10	12	13	13.5	14	15	16	18	20	22	24
Vital signs (blood pressure, pulse) a, b	X c	X		X		X	X	X	X	X	X		X		X	X	X	X	X d
ECG (12-lead) a, e	X c	X		X		X	X	X	X	X	X		X		X	X	X	X	X d
IP administration																			X d
PK blood sampling																			X d
PD blood sampling f	X c		X			X	X	X	X	X		X			X				X d
PD urine sampling g, h	X i	→	→	→	→	→	→	→	→	→	→	→	→	→	→	→	→	→	X d

a An attempt to perform these assessments and procedures should be made for any subject who withdraws or is removed from the study.

b Vital signs should be collected in the supine position at each time point. Subject should also be supine at least 5 minutes prior to vitals collection. Vital signs include blood pressure and pulse.

c These assessments should be performed within 30 minutes prior to the relative time of scheduled administration of IP on Day 1.

d Refer to Detailed Schedule of Assessments (Table 3 and Table 4) for collection time points (note: this time point is the same as the pre-dose collection time point on Day 1).

e ECGs will be performed in triplicate measurement at each time point.

f PD blood sampling assessments will include: total serum calcium, magnesium, phosphate, albumin, creatinine, 1,25-dihydroxyvitamin D, and FGF23.

g 24- hour urine collection for PD analysis will be collected according to the following collection intervals (relative to the Day 1 morning dose): pre-dose, 0-3 hours, 3-6 hours, 6-9 hours, 9-12 hours, 12-15 hours, 15-18 hours, 18-24 hours. ‘X’ denotes the start and stop of the entire urine collection period and ‘→’ denotes continuous collection.

h PD urine collection assessments will include: calcium, sodium, citrate, phosphate, magnesium, cAMP and creatinine.

i The predose timepoint for PD urine sampling is used to signify the action that the subject needs to empty his/her bladder immediately before the start of the 0-3 urine collection based on the predicted dosing time of Day 1. It is not a separate pre-dose urine collection.

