Table 3: Detailed Schedule of Assessments: Treatment Periods 1 and 2, Day 1/Day 2 (QD Regimen)																						
Study Day	1																				2	
Time point (relative to dosing time on Day 1) (h=hour/m=minute)	Pre-dose	0	10m	20m	30m	1	1.5	2	4	6	8	10	12	13	13.5	14	16	18	20	22	24	
Vital signs (blood pressure, pulse) a, b	X c					X		X	X	X	X	X	X	X		X	X	X	X	X	X	X j
ECG (12-lead) a, d	X c					X		X	X	X	X	X	X	X		X	X	X	X	X	X	X j
Randomization	X e																					
IP administration		X																				
PK blood sampling	X c		X	X	X	X	X	X	X		X		X				X					X
PD blood sampling f	X c						X		X	X	X	X	X		X		X		X			X
Anti-PTH antibody sampling g	X c																					
PD urine sampling h, i	X k	→	→	→	→	→	→	→	→	→	→	→	→	→	→	→	→	→	→	→	→	X

a An attempt to perform these assessments and procedures should be made for any subject who withdraws or is removed from the study.

b Vital signs should be collected in the supine position at each time point. Subject should also be supine at least 5 minutes prior to vitals collection. Vital signs include blood pressure and pulse.

c These assessments should be performed within 30 minutes prior to the scheduled time for IP dose administration on Day 1.

d ECGs will be performed in triplicate measurement at each time point.

e Randomization will occur prior to administration of IP of Treatment Period 1, Day 1 only (and only after all eligibility criteria have been confirmed/re-confirmed).

f PD blood sampling assessments will include: total serum calcium, magnesium, phosphate, albumin, creatinine, 1,25-dihydroxyvitamin D, and FGF23.

g The anti-PTH antibody sample should only be collected at Treatment Period 1, pre-dose (regardless of BID or QD regimen), and the sample collected within 30 mins prior to dosing.

h 24- hour urine collection for PD analysis will be collected according to the following collection intervals: 0-3 hours, 3-6 hours, 6-9 hours, 9-12 hours, 12-15 hours, 15-18 hours, 18-24 hours. ‘X’ denotes the start and stop of the entire urine collection period and ‘→’ denotes continuous collection.

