**Table 4: Detailed Schedule of Assessments: Treatment Periods 1 and 2, Day 1/Day 2 (BID Regimen)**

Study Day	1																					2							
Time point (relative to first dosing time on Day 1) (h=hour/m=minute)	Pre- dose	0	10m	20m	30m	1	1.5	2	4	6	8	10	Pre- dose (12hr)	12	12h 10m	12h 20m	12.5	13	13.5	14	16	18	20	22	24	28	32	36	
Vital signs (blood pressure, pulse) a, b	X c					X		X	X	X	X	X	X c					X		X	X	X	X	X	X	X	X	X	X k
ECG (12-lead) a, d	X c					X		X	X	X	X	X	X c					X		X	X	X	X	X	X	X	X	X	X k
Randomization	X e																												
IP administration		X												X															
PK blood sampling	X c		X	X	X	X	X	X	X		X		X f		X	X	X	X	X	X	X		X		X	X		X	
PD blood sampling g	X c						X		X	X	X	X	X f						X		X	X	X	X	X	X		X	
Anti-PTH antibody sampling h	X c																												
PD urine sampling i, j	X l	→	→	→	→	→	→	→	→	→	→	→	→	→	→	→	→	→	→	→	→	→	→	→	→	→	→	→	X

a An attempt to perform these assessments and procedures should be made for any subject who withdraws or is removed from the study.  
b Vital signs should be collected in the supine position at each time point. Subject should also be supine at least 5 minutes prior to vitals collection. Vital signs include blood pressure and pulse.  
c These assessments should be performed within 30 minutes prior to the scheduled time for IP dose administration on Day 1.  
d ECGs will be performed in triplicate measurement at each time point.  
e Randomization will occur prior to administration of IP of Treatment Period 1, Day 1 only (and only after all eligibility criteria have been confirmed/re-confirmed).  
f Pre-dose PK/PD collection for the second dose of the BID regimen should be completed within 15 minutes prior to the dose.  
g PD blood sampling assessments will include: total serum calcium, magnesium, phosphate, albumin, creatinine, 1,25-dihydroxyvitamin D, and FGF23.  
h The anti-PTH antibody sample should only be collected at Treatment Period 1, pre-dose (regardless of BID or QD regimen), and the sample collected within 30 mins prior to dosing.

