18-24 hours	20 hours/24 hours a
24-30 hours b	28 hours
30-36 hours b	36 hours

a 20 hours for Day 1, 24 hours for Day -1

b For BID dose groups only.

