#### 12.4.5 Statistical Analysis of Pharmacodynamic Data

For serum pharmacodynamic evaluations, concentrations (raw and baseline-adjusted) of serum total calcium and albumin-corrected calcium, phosphate, creatinine, magnesium, 1,25(OH)2D3 and FGF23 will be summarized with descriptive statistics (number, arithmetic mean, SD, CV%, median, minimum, and maximum) by treatment and day. Pharmacodynamic parameters of serum total calcium and albumin-corrected calcium, phosphate, magnesium, 1,25(OH)2D3 and FGF23 will be summarized with descriptive statistics (number, arithmetic mean, SD, CV%, median, minimum, maximum, geometric mean, and geometric CV%) by treatment and day. This will be done for both raw and baseline-adjusted values, and will be done for both Day -1 and Day 1/2. Note for the Day -1 summaries, the treatment assigned will be the treatment the subject takes the following day.

Individual and mean concentration (raw and baseline-adjusted)-time plots of serum pharmacodynamic markers (serum total calcium and albumin-corrected calcium, phosphate, creatinine, magnesium, 1,25(OH)2D3 and FGF23) will be generated on both linear and semilog scales. These figures will be generated as overlay plots by treatment.

For urine pharmacodynamic evaluations, the individual urinary excretion of calcium, sodium, citrate, magnesium, cAMP, and phosphate and amount relative to creatinine of calcium, sodium, citrate, magnesium, cAMP and phosphate in each collection period as well as over 24 hours will be listed and summarized with descriptive statistics by treatment and day (Day -1 and Day 1/2).

In addition, the renal clearance of calcium, magnesium,, creatinine and phosphate and fractional excretion of calcium, magnesium and phosphate in each collection period will be summarized with descriptive statistics by treatment and day.

Individual and mean urine pharmacodynamic parameters over time (urine collection interval) will be plotted on a linear scale, overlaid by treatment (both Day -1 and Days 1 and 2 will be presented on the same plot).

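### Serum PD sampling from 16 to 24 h differs between Day -1, QD and BID, so the Day -1 and Day 1 0-24 h parameters tabulated side by side can differ because of the sampling times alone

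*SAP*

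**What the plan says.** SAP 12.4.3 derives AUC0-24h, Emax, Emin and their times from raw serum concentrations. From baseline-adjusted concentrations it derives AUCabove, AUCbelow, AUCnet and the same extremes. It states that "pharmacodynamic parameters will be estimated for both Day -1 and Day 1 in each treatment period". SAP 12.4.5 then summarises raw and baseline-adjusted parameters by treatment and day, and says this "will be done for both Day -1 and Day 1/2". Neither section restricts the parameters to sampling times that the profiles share.

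The detailed schedules in SAP 2.4 give these serum PD times:

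- **Day -1:** predose, 1.5, 4, 6, 8, 10, 12, 13.5 and 16 h, then 24 h. A footnote explains the last point: "this time point is the same as the pre-dose collection time point on Day 1".
- **QD, Day 1:** the same times plus 20 h.
- **BID, Day 1/2:** the same times plus 18, 20 and 22 h, then 28 and 36 h.

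The SAP recognises the Day -1 gap in one place. For renal clearance and fractional excretion over 18-24 h (SAP 12.4.4), the matched serum value is "20 hours for Day 1, 24 hours for Day -1". There is no equivalent provision for the serum parameters.

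**The concern.** Control of serum calcium is part of the primary objective, and Day -1 is the only 24-hour serum profile without study drug. A reader of the tables will naturally set the Day 1 AUC0-24h, Emin or Emax beside the Day -1 value. On Day -1 the last third of the window is a single straight line from 16 to 24 h, and no extreme between those times can be recorded. On Day 1 the same interval is sampled once (QD) or three times (BID). An overnight excursion present on both days would enter the Day 1 parameters and not the Day -1 parameters, and part of the apparent Day 1 change would come from the schedule.

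**Working it through.** **1. Reproduce the plan's counts.** From the SAP schedules, Day -1 has 9 samples of its own (the 24 h point is the Day 1 predose sample), QD has 11 and BID has 15. Protocol Table 6 gives the same figures: 9 per period on Day -1 (9 + 9 = 18), and 11 + 15 = 26 for Days 1-2. Samples strictly between 16 and 24 h number 0, 1 and 3. The 20 h position for QD is taken from the SAP's QD schedule and agrees with the footnote to the urine-matching table.

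**2. Weights at the end of the window.** Under the linear trapezoid, a sample's weight is half the sum of the intervals on either side. SAP 12.4.3 names this rule for the baseline-adjusted areas and gives none for the raw area.

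| Profile | Weight of 16 h sample | Weight of 24 h sample |
|---|---|---|
| Day -1 | 2.5/2 + 8/2 = 5.25 h | 8/2 = 4 h |
| QD | 2.5/2 + 4/2 = 3.25 h | 4/2 = 2 h |
| BID | 2.5/2 + 2/2 = 2.25 h | 2/2 = 1 h |

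**3. One identical overnight dip on every profile.** Assume no drug effect and a half-sine dip of depth d from 16 to 24 h. Its value is d at 20 h and 0.707d at 18 and 22 h. The recorded areas are:

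- Day -1: 0
- QD: -(4 × d/2 + 4 × d/2) = -4d
- BID: -2 × (0.707 + 1 + 0.707)d = -4.83d
- True area: -16d/π = -5.09d

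| d (mmol/L, assumed) | QD minus Day -1 | BID minus Day -1 | BID minus QD |
|---|---|---|---|
| 0.02 | -0.08 | -0.10 | -0.02 |
| 0.05 | -0.20 | -0.24 | -0.04 |
| 0.08 | -0.32 | -0.39 | -0.07 |

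Differences are in mmol.h/L. Subtracting a constant baseline within each day does not change the curvature term, so the same artefact carries into AUCnet.

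**4. Scale.** Protocol 2.1 reports a maximum mean rise of 0.125-0.175 mmol/L at 12 h after once-daily dosing, not back to baseline at 24 h. Assume a straight rise to the peak p at 12 h and a straight fall to a fraction r of the peak at 24 h, with r = 0.3-0.5. The area is 6p + 6p(1 + r) = 6p(2 + r).

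- Smallest: 6 × 0.125 × 2.3 = 1.7 mmol.h/L
- Largest: 6 × 0.175 × 2.5 = 2.6 mmol.h/L

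At d = 0.05 the QD artefact is 0.20/2.6 to 0.20/1.7, about 8-12% of this area. The documents give no BID effect, so no such percentage is given for BID.

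**5. Other shapes, at an assumed depth of 0.10 mmol/L.**

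| Shape | QD minus Day -1 | BID minus Day -1 | BID minus QD |
|---|---|---|---|
| Straight drift, 16-24 h | 0 | 0 | 0 |
| Triangle centred at 20 h | -0.40 | -0.40 | 0 |
| Plateau, 18-22 h | -0.40 | -0.60 | -0.20 |
| Short dip at 18 or 22 h | 0 | -0.20 | -0.20 |

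**6. Extremes.** Day -1 records none of a dip between 16 and 24 h. QD and BID both record its full depth if it is centred at 20 h; only BID does if it is a short dip at 18 or 22 h. Emin changes only if the dip is the lowest point of the whole profile. Emax changes only for a rise that is the highest point.

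**The case against.** The strongest reply is that the SAP plans no Day 1 minus Day -1 contrast. SAP 2.5 and 2.6 describe the analyses as primarily descriptive, with no hypothesis testing, and SAP 12.4.2 gives each day its own baseline. This stands: the harm is to descriptive reading, and no error rate is involved.

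Day -1 is also not a clean control. Under Protocol 3.1 all subjects take their usual calcium and active vitamin D on Day -1. On Day 1 vitamin D is withheld for everyone, and calcium is withheld in Treatments A, B and C. Matching the sampling times would not turn the day-to-day difference into a pure drug effect.

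Several stronger readings are tempting and are not supported:

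- **That the QD versus BID comparison is seriously distorted.** For the half-sine dip of 0.05 mmol/L the difference is 0.04, about 2% of the assumed QD area. It is larger only for particular shapes.
- **That the unequal times make every area much noisier on Day -1.** For raw AUC0-24h the noise SD is 8.5, 7.7 and 6.8 times the single-sample SD (Day -1, QD, BID). For AUCnet, subtracting the predose value gives that sample a weight of 0.75 - 24 = -23.25 h, and the multipliers become 24.7, 24.5 and 24.2, practically equal.
- **That the schedule contradicts Amendment 1.** The log records that on Day -1 "PD blood collections were removed at 18, 20, and 22 hours post-dose time points". It describes past changes, so a mismatch with the current schedule is not an error.

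Finally, time-point summaries and overlay plots by treatment and day already allow time-matched reading at shared times. That helps with concentrations but leaves the derived parameters as they are.

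**Conclusion.** The point holds as a limited one about presentation. The sampling differences are exact, and the SAP places the same 0-24 h parameters side by side without allowing for them. The size is conditional: it rests on an assumed non-linear overnight change, identical on all days, for which the documents give no amplitude or shape. Under a half-sine dip of 0.02-0.08 mmol/L, the artefact in Day 1 minus Day -1 AUC0-24h is -0.08 to -0.32 (QD) and -0.10 to -0.39 mmol.h/L (BID). That matters against an effect area of about 2 mmol.h/L. It is small against the raw area: with calcium flat at an assumed 2.1 mmol/L, raw AUC0-24h is 24 × 2.1 = 50.4, and 0.20 is 0.4% of it. The documents do not show that an overnight change of this kind occurs, or that the planned tables would be wrong if it does not.

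**What to change.** In SAP 12.4.3, keep the full-schedule parameters as planned and add a matched-time version for reading across profiles, still calculated with actual sampling times:

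- **Day 1 versus Day -1:** samples at the ten shared nominal times (0, 1.5, 4, 6, 8, 10, 12, 13.5, 16 and 24 h).
- **BID versus QD:** samples at the eleven shared nominal times, which add 20 h.

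Report both versions. Add a note to the tables that Day -1 has no serum PD samples between 16 and 24 h and that supplements also differ between the days. With matched nominal times an identical overnight change cancels, apart from small deviations in actual times.

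The cost is SAP wording and one extra run. The real downside is that the matched version does not show drug effects at the unshared times. In the ten-point version, 16-24 h (4 to 12 h after the second BID dose) becomes a straight line. In the eleven-point version, the BID samples at 18 and 22 h are not used. For that reason the matched version should sit beside the full-schedule one and not replace it.

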**Rationale:**

This study is being conducted to characterize the effect of twice-daily administration of rhPTH(1-84) on pharmacokinetics, pharmacodynamics, safety and tolerability over the course of 24-36 hours as compared with the currently approved once-daily dosing regimen, with and without oral calcium and without active vitamin D.

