**Pharmacokinetic Endpoints:**

PTH concentrations will be used to calculate the following pharmacokinetic parameters using a non-compartmental approach: maximum observed concentration maximum ( $C_{max}$ ), time of maximum concentration ( $T_{max}$ ), area under the concentration curve (from time zero to the last measurable concentration and from time zero to infinity ( $AUC_{0-t}$  and  $AUC_{0-inf}$ ), area under the concentration curve from time zero to 24 hours post the first dose ( $[AUC_{0-24h}]$  for those on the QD regimen, and up to 24 hours post the second dose for those on the BID regimen), elimination rate constant ( $K_{el}$ ), apparent clearance ( $CL/F$ ), apparent volume of distribution ( $V_z/F$ ) and elimination half-life ( $t_{1/2}$ ).

All assessment dates will be related to the first day of rhPTH(1-84) administration. This first day of investigational product administration is referred to as Day 1. Day-1 is the day that is preceding Day 1, and a Day 0 will not be defined.

Pharmacokinetic analyses based on raw and baseline-adjusted PTH concentrations will be performed. The baseline is defined as the predose endogenous PTH level on Day 1, and baseline-adjusted PTH concentrations are to be calculated by subtracting baseline PTH from the raw PTH concentrations.

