## 2. STUDY OBJECTIVES AND PURPOSE

### 2.1 Rationale for the Study

Recombinant human PTH (rhPTH[1-84]) is approved for use in the US as an adjunct to calcium and vitamin D to control hypocalcemia in patients with hypoparathyroidism. As a once-daily SC injection for hypoparathyroidism it has been shown to provide a 24-hour sustained increase in serum calcium. Administration of rhPTH(1-84) resulted in dose-related increases in total serum calcium levels with maximum mean increases (approximately 0.125 to 0.175 mmol/L) observed 12 hours after dosing. Serum calcium levels did not return to baseline levels by 24 hours. This sustained increase may explain the reduction in the observed daily amounts of calcium and active vitamin D that were taken in the placebo-controlled trial.

Other clinical studies have reported experience with twice-daily use of a fragment of PTH (PTH[1-34]) injected SC in the setting of adult and pediatric subjects with hypoparathyroidism (Winer et al., 1998; Winer et al., 2003; Winer et al., 2008). In this setting, PTH(1-34) maintained eucalcemia and reduced urinary calcium excretion. In these studies, a comparison with calcitriol showed that either twice-daily PTH(1-34) or twice-daily calcitriol each maintained similar serum calcium levels, although urinary calcium excretion was lower in the PTH(1-34)-treated subjects.

The present study is being conducted to characterize the effects of twice-daily administration of rhPTH(1-84) on pharmacokinetics, pharmacodynamics, safety and tolerability over the course of 24 hours as compared with the current once-daily dosing regimen.

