On Day 1 of Treatment Period 2, subjects will receive the alternative treatment (according to the randomization schedule), following a washout period ( $\geq 5$  days [ie, 120 hours] and  $\leq 30$  days) between administration of the dose or first dose ([for once-daily or twice-daily dosing, respectively] of each treatment period). All investigational product will be administered via SC injection into alternating thighs at each administration.

At each treatment period, subjects will report to the CRC on Day-2, remain in the CRC through Day 2, and be discharged following the last scheduled assessment on Day 2 (investigators may elect, at their discretion, to keep the subject in-clinic after Treatment Period 1 for the duration of the washout period, eg, if the washout period is short [eg, 120-172 hours] or there are any safety concerns).

For once-daily treatments (Treatments B and E), subjects will receive a single subcutaneous dose of rhPTH(1-84) in the morning on Day 1. For twice-daily treatments (Treatments A, C, D, and F), subjects will receive a subcutaneous dose of rhPTH(1-84) in the morning followed by the second dose 12 hours later on Day 1 (in the opposite thigh). If randomized to rhPTH(1-84) with calcium, subjects will take their usual supplemental oral calcium on Day 1 per their usual schedule. Prior to discharge from the CRC at each treatment period, subjects will be given specific instructions for when to take their supplemental oral calcium and active vitamin D supplements during the day(s) when subjects are not in the CRC.

Subjects enrolled in the study must require daily doses of calcium supplements of  $\geq 1000$  mg prior to baseline (Day 1). Subjects enrolled in the study must also require minimum daily doses of active vitamin D of  $\geq 0.25\mu\text{g}$  (ie,  $0.25\mu\text{g}$  calcitriol or equivalent). Subjects will be expected to adhere to standard meals provided during their confinement in the CRC during each period (from check-in on Day -2 until discharge on Day 2). All subjects (in all treatments) will take their usual doses at the usual regimen of supplemental oral calcium and active vitamin D on Day -2 and Day -1. For all subjects in all cohorts, active vitamin D supplements must be withheld on Day 1 through completion of all study procedures on Day 2. Subjects may resume active vitamin D following final procedures on Day 2 at the discretion or direction of the investigator.

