#### 12.4.4 Urinary Pharmacodynamic Parameters

The following parameters will be calculated for both Day -1 and Day 1/Day 2 in each treatment period:

- Total amount of sodium (mmol), calcium (mmol), magnesium (mmol), citrate (mmol), phosphate (mmol), cAMP (μmol) and creatinine (mmol) excreted in urine in each collection period where total amount = (total volume [L] of urine in each collection) × (concentration [mmol/L, mmol/L or μmol/L]) in pooled urine samples during a collection period
- Total amount of sodium, calcium, magnesium, citrate, cAMP and phosphate excreted in each collection period relative to the total amount of creatinine excreted in the same collection interval, mmol/mmol, nmol/mmol, or μmol/mmol
- Total amount of sodium, calcium, magnesium, citrate, phosphate, cAMP and creatinine excreted in urine over 24 hours post dose, mmol, nmol, or μmol
- Total amount of sodium, calcium, magnesium, citrate, phosphate and cAMP excreted in urine over 24 hours post dose relative to the total amount of creatinine excreted over 24 hours post dose, mmol/mmol, nmol/mmol, or μmol/mmol
- Renal clearance (CLr) of calcium, magnesium, creatinine and phosphate (mL/min) in each collection period where CLr = (Urine concentration) × (urine flow/serum concentration); urine flow is calculated as the total urine volume divided by time in the collection interval
- Fractional excretion (FE) of calcium, magnesium, and phosphate in each collection period, calculated as:

$$100 \times [\text{Urine concentration of the analyte} \times \text{Serum Creatinine}] / [\text{Serum concentration of the analyte} \times \text{Urine Creatinine}].$$

For the calculation of CLr and FE in each collection interval, the serum concentration value used is that which occurs at or closest to the middle of the urine collection period. For example, for the 0-3 hour urine collection, the serum values determined at the 1.5-hour serum sample is to be used. Calculation of these parameters will be by each time interval collected in

the CRF (0-3, 3-6, 6-9, 9-12, 12-15, 15-18, 18-24 hours for QD, and for BID this will also include 24-30, and 30-36 hours).

The following table shows the urine collection period and the corresponding timepoint to be used for the serum concentration:

Urine Collection Period	Timepoint of Collection of Serum Concentration
0-3 hours	1.5 hours
3-6 hours	4 hours
6-9 hours	8 hours
9-12 hours	10 hours
12-15 hours	13.5 hours
15-18 hours	16 hours

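### The baseline-adjusted serum areas stop 12 h after the second twice-daily dose, so read as the effect of the daily dose they understate 50 µg BID against 100 µg QD

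*SAP*

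**What the plan says.** SAP 12.4.3 gives the raw serum AUC0-24h as "the area under the concentration versus time curve, from time 0 to 24 hours". AUCabove is the area "that is above the baseline, from time 0 to 24 hours, as calculated by the linear trapezoidal method". AUCbelow has the same limits, and AUCnet is the difference of the two. The limits are the same for QD and BID.

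SAP 12.4.4 gives urine totals "excreted in urine over 24 hours post dose" and does not say which dose starts the clock in a BID period.

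In the BID treatments the morning injection is "followed by the second dose 12 hours later on Day 1" (Protocol 3.1). On timing of effect, Protocol 2.1 says that the maximum mean serum calcium increases, about 0.125 to 0.175 mmol/L, were "observed 12 hours after dosing. Serum calcium levels did not return to baseline levels by 24 hours".

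BID sampling runs past 24 h. SAP Table 4 (BID regimen) schedules serum pharmacodynamic samples at 28 and 36 h and urine at 24-30 and 30-36 h. The synopsis rationale describes a study "over the course of 24-36 hours as compared with the currently approved once-daily dosing regimen", and the synopsis pharmacokinetic endpoints take the area "up to 24 hours post the second dose for those on the BID regimen".

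**The concern.** Dosing lasts one day, so there is no steady state in which a 24-h window would capture a full dosing cycle. For QD, 0-24 h holds 24 h of response to the whole daily dose. For BID it holds 24 h of response to the first half and only 12 h of response to the second, and by the protocol's own figure 12 h is when the calcium effect peaks. The serum samples at 28 and 36 h enter no area, although SAP 4.5 excludes a whole period's pharmacodynamic data in Treatments A to C if supplements are taken within 24 h of the last dose, which for BID means up to 36 h.

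The primary objective covers control of serum calcium under 25 µg BID, 50 µg BID and 100 µg QD. The analysis is descriptive, so the summary tables are the result. A reader who takes the baseline-adjusted areas as the effect of a day's dosing would see a smaller effect for 50 µg BID than for 100 µg QD even if the split made no difference.

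**Working it through.** The plan has no calculation to reproduce here: it states no power, effect size or hypothesis test. The figure that matters is the 12-h peak in Protocol 2.1.

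**Inputs from the documents.** Second dose at 12 h. Area window 0-24 h. Peak increase 0.125 to 0.175 mmol/L at 12 h. Effect above baseline at 24 h, by an amount not given. Equal daily dose only for 50 µg BID against 100 µg QD (Cohorts 2 and 4).

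**Assumptions.** Effect proportional to dose and additive across doses. Underlying calcium constant. The effect of 100 µg rises linearly to 1 at 12 h and falls linearly to f at 24 h, with f from 0 to 1; the same slope then continues, not below zero.

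**Timing.** 24 − 12 = 12 h of second-dose response is inside the window. 12 + 24 = 36 h is the end of BID sampling.

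**Baseline-adjusted area, 0-24 h.**
- QD: 6 + 6(1 + f) = 12 + 6f.
- BID: 0.5(12 + 6f) + 0.5(6) = 9 + 3f.
- Ratio: (9 + 3f)/(12 + 6f).
- Share of the second dose's 24-h response that is counted: 6/(12 + 6f), or 50% at f = 0 and 33% at f = 1.

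With QD held at 0-24 h and no true regimen difference, the BID/QD ratio by BID window is:

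| f | BID 0-24 h | BID 12-36 h | BID 0-36 h |
|---|---|---|---|
| 0 | 9/12 = 0.75 | 0.75 | 1.00 |
| 0.5 | 10.5/15 = 0.70 | 0.90 | 1.10 |
| 1 | 12/18 = 0.67 | 1.17 | 1.33 |

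Example for BID 0-36 h at f = 0.5: the first dose contributes 0.5 × 18 and the second 0.5 × 15, so 16.5/15 = 1.10. No BID window gives a ratio of 1 across the range, because QD is itself cut at 24 h.

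**Checks.** Trapezoids on the scheduled sampling times give 0.750, 0.700 and 0.672 for f = 0, 0.5 and 0.9. Gamma-shaped profiles peaking at 12 h give a shortfall of 28% to 29%. The peak time drives the size. With gamma shapes peaking at 2, 4, 6 and 8 h, the shortfall is 0%, 0-3%, 5-11% and 14-19%.

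**Raw AUC0-24h.** The absolute shortfall is peak × (3 + 3f): from 0.125 × 3 = 0.375 to 0.175 × 6 = 1.05 mmol·h/L. To scale it, assume a calcium level in the 7.5 to 10.6 mg/dL range of the Phase 3 endpoint (Protocol 1.2.2). The protocol's equivalence of 200 mg and 5 mmol gives 40 mg per mmol, so the range is about 1.875 to 2.65 mmol/L.
- Smallest: 0.375/(24 × 2.65 + 0.125 × 12) = 0.375/65.1 = 0.6%.
- Largest: 1.05/(24 × 1.875 + 0.175 × 18) = 1.05/48.15 = 2.2%.

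**Urine.** The documents give no time of peak effect for urinary calcium, and the BID reference dose is open: 0-24 h and 12-36 h both fit the wording. No size can be derived.

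**The case against.** The best defence is that a common 0-24 h window is a proper choice. Protocol 2.1 states the aim as comparing the regimens over 24 hours, Protocol 9.8.2.1 itself specifies AUC0-24h, and Protocol 9.8.1 and SAP 12.3.3 run the pharmacokinetic AUC0-24h from the first dose too. That stands: for the effect in the first 24 h the areas are correct. It also weakens the contrast with the synopsis pharmacokinetic window. What it leaves open is that the synopsis rationale speaks of 24 to 36 hours, and the SAP does not say which reading its areas serve.

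Four stronger readings are tempting, and the documents do not support them.
- **That every area is a quarter to a third too low.** This fails for raw AUC0-24h, where the calcium level itself dominates.
- **That the urine totals are understated in the same way.** The 12-h peak is for serum calcium only, the totals are absolute amounts and not effects above baseline, and the reference dose is unnamed. That is an ambiguity, not a demonstrated truncation.
- **That QD is fully sampled and only BID is cut.** Calcium had not returned to baseline at 24 h, so the QD tail is lost too.
- **That the late BID data are discarded.** SAP 12.4.5 summarises concentrations and per-interval urine amounts for Day 1/2. SAP 12.4.4 computes renal clearance and fractional excretion to 36 h. Emax and Emin carry no stated 24-h limit. The gap is a summary area covering the second dose.

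It is also fair that simply lengthening the BID window would mislead. For raw areas and urine totals, 36 h against 24 h adds about 50% from clock time alone (36/24 = 1.5).

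**Conclusion.** The point holds for AUCabove, AUCbelow and AUCnet in SAP 12.4.3, read as the effect of the daily dose. For serum calcium, 50 µg BID would then appear about 25% to 33% below 100 µg QD in Cohorts 2 and 4 with no true difference. The size rests on linear, dose-proportional superposition, the protocol's 12-h peak, a 24-h residual of 0% to 100% of peak, and a constant underlying calcium level. The last is doubtful: active vitamin D is withheld from Day 1 in all treatments, and oral calcium as well in Treatments A to C. Raw AUC0-24h is affected by only about 0.6% to 2.2%.

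This is an inexpensive improvement to a descriptive study, not an error in the 0-24 h parameters.

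**What to change.** In SAP 12.4.3 and 12.4.4:

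1. Keep the 0-24 h parameters and state that they run from the first dose. Name the reference dose for the BID urine totals over 24 hours.
2. Add as supplementary, for BID, baseline-adjusted AUCabove, AUCbelow and AUCnet over 0-36 h, labelled as running to 24 h after the last dose.
3. Add, for both regimens, serum areas and urine amounts over 0-12 h and 12-24 h, plus 24-36 h for BID. The scheduled samples and collection intervals already break at these times, and SAP 12.3.3 already makes the 12-h split for BID pharmacokinetics.
4. Do not set BID 0-36 h raw areas or urine totals directly beside QD 0-24 h. Show them per interval or as a rate per hour.
5. Footnote the tables: BID 0-24 h covers only 12 h after the second dose; the QD tail is also cut at 24 h, so baseline-adjusted BID 0-36 h against QD 0-24 h can favour BID (1.00 to 1.33 under the model above); and the 24-36 h segment reflects longer supplement withholding and has no Day -1 counterpart.

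The cost is SAP wording, a few more parameters in the WinNonlin run and extra table rows. No new samples or visits are needed. The downside is a supplementary comparison that cannot be read without its caveats.
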